## Statistical analysis

All statistical analysis were performed using Statistical Package for Social Sciences (SPSS) for Windows software version 23. Numerical variables were expressed as mean  $\pm$  SD or median (minimum–maximum). Categorical variables were expressed as frequency (%). Test of normality was done using Kolmogorov–Smirnov test. One-Way analysis of variance (ANOVA) was used to compare means if data distribution was normal, or nonparametric test Mann-Whitney U was used if data was not distributed normally. Pearson chi-square or Fischer's exact test was used for assessing categorical variables. Log rank test was used to evaluate the time difference in the first administration of diclofenac sodium after surgery, and hazard ratio (HR) was used to evaluate the benefit. All tests were two-tailed, and the significance level was set at  $\alpha$  0.05.

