3.1.3 Exclusion criteria

- 1) Severe obesity ($BMI > 35 \text{ kg/m}^2$);
- 2) Spinal deformity or surgical history;
- 3) Allergic to local anesthetics;
- 4) There are coagulation disorders;
- 5) Communication barriers

4. Research process

1. Preoperative records

Patients were visited according to clinical routine on the day before surgery, and their age, gender, height, weight, ASA grade, and operation name were recorded. Patients were identified according to inclusion and exclusion criteria, informed consent was signed, and basic patient information was recorded.

2. Anesthesia protocol and intraoperative records

Based on a computer-generated table of random numbers, they were randomly assigned to receive combined lumbar and epidural anesthesia in either the US-AS group (n=48) or the US-RTG group (n=48). Patient assignments are hidden by sequentially numbered and sealed opaque envelopes that can only be opened by the attending anesthesiologist when the patient enters the operating room. Patients know nothing about grouping. Neither the intraoperative parameter collector nor the anesthesiologist performing the procedure can blind the groups.

All ultrasound-guided CSEA blocks were performed by an attending anesthesiologist (>100 cases per year) who was skilled in ultrasound-assisted and real-time ultrasound-guided intra spinal block, and another attending physician who was familiar with the procedure was responsible for parameter recording. When the patient enters the room, connect the monitor. Nasal catheter oxygen (oxygen flow 3 L/min) to establish peripheral venous access. 1. Assess the difficulty of palpating the spinous process (1 degree: easy - slight or moderate pressure on the tissue; Grade 2: moderately significant tissue compression; 3 degrees: Difficult/unable to palpate). 2. If the patient could not cooperate due to hip pain, iliofascial space block (20mL, 0.4% ropivacaine) was performed in the supine position, and 15min later, the patient lay on his side (affected side up).

In the US-AS group, the intraspinal structure was evaluated using a portable ultrasonic system (Sonosite, low frequency convex array probe 2-5 MHz) (ultrasonic prescan to determine the best intervertebral space, best puncture Angle and best puncture depth). The measurement methods (in-plane measurement of paracentral transverse section (LTP), out-of-plane measurement of paracentral sagittal section (LSC) and in-plane measurement

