The maximum number of skin puncture should be 6 times, and the cumulative redirection of each skin puncture should not exceed 6 times. If six skin piercings are unsuccessful, traditional palpation, replacement of puncture Spaces, or general anesthesia are considered and recorded.

Whether the patient was in the left or right decubitus position, the operator used the puncture needle manually and the ultrasound probe non-manually. Adverse reactions and complications were recorded in both groups, including radicular pain, bloody cerebrospinal fluid puncture, headache after dural puncture, paresthesia, back pain, whether traditional palpation was used, the puncture space was changed, or general anesthesia was used. Patient satisfaction score: Patients were asked to use a 5-point numerical rating scale to evaluate their satisfaction (1, very dissatisfied; 5, very satisfied). The VNRS, verbal numerical rating scale (0-10) and whether to add analgesic drugs were recorded in the two groups.

3. Outcomes

Primary outcomes: first attempt success rate (first skin piercing, no redirection);

Secondary outcomes: operation time (seconds), positioning time, depth and width of posterior dural complex, skin puncture number, redirection number;

Patient satisfaction score: Patients were asked to use a 5-point numerical rating scale to evaluate their satisfaction (1, very dissatisfied; 5, very satisfied).

Operation difficulty score: After the operation, the anesthesiologist will score the difficulty of this operation (1, very dissatisfied; 5, very satisfied). Change of anesthesia method (traditional blind method, USAS or USRTG, change of puncture space, general anesthesia).

Adverse reactions and complications: include radicular pain, bleeding, puncture, headache after dural puncture, paraesthesia, and back pain.

Reference

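### The SAP plans a log-rank test and hazard ratio for time to first diclofenac after surgery, an endpoint the protocol does not declare

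*SAP*

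**What the plan says.** The SAP's Statistical analysis section assigns most methods by type of variable: one set for numerical data and one for categorical data. One sentence is different because it names an endpoint: "Log rank test was used to evaluate the time difference in the first administration of diclofenac sodium after surgery". The effect measure follows: "hazard ratio (HR) was used to evaluate the benefit". The section closes with a general rule, "All tests were two-tailed, and the significance level was set at" 0.05, and makes no exception for this analysis.

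The protocol's Outcomes (section 4, item 3) open with "Primary outcomes: first attempt success rate (first skin piercing, no redirection" and continue with "Secondary outcomes: operation time (seconds), positioning time, depth and width of posterior dural complex, skin puncture number, redirection number". The rest of the list consists of patient satisfaction, difficulty as scored by the operator, change of anesthetic method, and complications. Analgesic use appears only in section 4, item 2, where a verbal pain score and "whether to add analgesic drugs were recorded in the two groups".

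**The concern.** A log-rank comparison with a hazard ratio is a full efficacy analysis with its own endpoint. Here the endpoint is time to a named analgesic after surgery, in a trial that compares two ways of guiding a needle. Section 2 of the protocol states a general aim of comparing clinical effect and says nothing about duration of analgesia.

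From the text available, a reader cannot tell whether an intended endpoint was left out of the protocol or whether the sentence does not belong to this trial. If the analysis is run as written, a result on an endpoint the protocol never declared could be reported at the ordinary significance level as evidence of benefit. There would be no protocol definition to hold it to. What is at stake is the credibility of that one result and the agreement of the two documents. The primary comparison is not at stake.

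**Working it through.** **1. What the trial was sized for.** Protocol section 3.1.1 gives first-puncture success of 80.7% against 52.6%, two-sided alpha 0.05, 80% power and 10% dropout. The two-proportion formula with pooled variance under the null is

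n = [1.960·√(2·p̄·(1−p̄)) + 0.842·√(p1(1−p1) + p2(1−p2))]² / (p1−p2)²

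with p̄ = (0.807 + 0.526)/2 = 0.6665 and p1−p2 = 0.281.

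- First term: 1.960 × √0.4446 = 1.307.
- Second term: 0.842 × √(0.1558 + 0.2493) = 0.842 × √0.4051 = 0.536.
- n = (1.307 + 0.536)² / 0.0790 = 43.0, so 43 per group.
- Dropout: 43/0.90 = 47.8, so 48 per group and 96 in total.

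The stated figures reproduce. They rest only on the binary primary outcome. No hazard ratio, event count or follow-up time enters the design.

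**2. Is diclofenac anywhere in the protocol?** No. The drugs named are ropivacaine (section 4, item 2), ephedrine (in the background, for a cited study) and bupivacaine (in the title of a reference). The protocol names no postoperative analgesic.

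**3. Is any declared outcome a time to event?** Taking the Outcomes list in turn:

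- First-attempt success: binary.
- Operation time and positioning time: durations of the procedure itself. Section 4, item 2 starts operation time when the probe touches the skin and ends it with the procedure.
- Depth and width of the dural complex: measurements.
- Skin punctures and redirections: counts.
- Satisfaction and difficulty: 5-point scores.
- Change of method and complications: occurrence only.

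None is a time from surgery to an event.

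**4. What the planned analysis needs, and what the protocol specifies.** A log-rank test and hazard ratio need four things for each patient.

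- Time origin: the SAP says only after surgery. The protocol gives none.
- Event and its time: the SAP says first diclofenac dose. The protocol records whether analgesics were added, with no drug named and no time.
- Follow-up window: not given in the protocol or in the SAP's Statistical analysis section.
- Censoring rule for patients who receive none: likewise not given.

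The mismatch follows from the text alone and depends on no assumed rate or effect.

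**The case against.** The strongest reply is that the effect is small. The primary analysis is untouched, the protocol does record pain scores and added analgesics, and the SAP may simply be more specific about data that exist. Part of this stands: the primary result does not change, and dose times may well be held in the anesthetic or ward record. But a yes/no note is not a declared outcome, and it supplies none of the definitions in step 4.

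A second reply is that one part of the SAP document was not available. It may bear on how the endpoint entered the SAP, so its origin should be left open. It cannot put the endpoint into the protocol.

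Several stronger readings are tempting, and the documents do not support them.

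- A reader might infer that the analysis cannot be run. The documents show only that the protocol specifies no dose time, not that none is recorded.
- A reader might take the heading "Anesthesia protocol and intraoperative records" to show that analgesic use was recorded only during surgery or was never meant for analysis. The same section also records headache after dural puncture, back pain and satisfaction, all of which reappear as outcomes.
- A reader might infer a serious rise in false-positive risk. The primary test keeps its own 5% level, and the SAP already tests many other outcomes at 0.05. The defect is an undeclared endpoint, not multiplicity.
- A reader might call the analysis underpowered. The documents give no event rate or hazard ratio from which to judge that, and the mismatch would be the same with ample power.

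**Conclusion.** The point holds as an inconsistency between the two documents. The SAP plans a time-to-event efficacy analysis that matches no outcome in the protocol, and the protocol specifies none of the elements needed to define it. The effect on the primary result is nil. The consequence is confined to one analysis, which as written would test an undeclared endpoint at two-sided 0.05 and describe the result as benefit. It is a minor consistency correction.

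The conclusion rests on the complete protocol text and on the SAP's Statistical analysis section. It does not depend on whether dose times exist, on how often diclofenac was given, or on the part of the SAP that was not available. A reader might go further and conclude that the sentence was carried over from another study. The documents do not show where it came from.

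**What to change.** Reconcile the protocol and the SAP; which route applies depends on whether the endpoint belongs to this trial.

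- If it does not, delete the log-rank and hazard-ratio sentence from the SAP. This costs one sentence, with no extra patients and no change to data collection.
- If it does and dose times are recorded, declare time to first postoperative diclofenac in both documents as exploratory. State the time origin, the follow-up window and how patients who receive none are censored, and drop the description of the hazard ratio as a measure of benefit. This costs a short paragraph in each document and requires a dose time and an end of follow-up for each patient.

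The sample size and the primary analysis need no change under either route.
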